5.2. Exclusion Criteria

Participants are excluded from the study if any of the following criteria apply:

Medical Conditions

1. Have a positive pregnancy test at screening or Day -1, where applicable
2. Are planning to become pregnant during the study or within 1 month of study completion
3. Are women who are lactating
4. Have known allergies to selpercatinib-related compounds or any components of the formulation of selpercatinib, or history of significant atopy
5. Have a history of allergic reactions to medications or food products
6. Have a clinically significant abnormality of blood pressure and/or pulse rate as determined by the investigator
7. Clinically significant abnormalities on ECG as determined by the investigator or prolongation of the QTcB or QTcF >450 msec at screening
8. Have clinically significant active cardiovascular disease or history of myocardial infarction within 6 months prior to the planned start of selpercatinib

9. Have a history or presence of cardiovascular, respiratory, renal, gastrointestinal, endocrine, hematological, or neurological disorders capable of significantly altering the absorption, metabolism, or elimination of drugs; of constituting a risk when taking the investigational product; or of interfering with the interpretation of data. Appendectomy, splenectomy, and cholecystectomy are considered as acceptable
10. Have a creatinine clearance <60 mL/min, as calculated using the CKD-EPI equation (Levey et al, 2009).

$$\text{eGFR} = 141 \times \min(\text{Scr}/\text{K}, 1)^\alpha \times \max(\text{Scr}/\text{K}, 1)^{-1.209} \times 0.993 \text{age}$$

$$\times 1.018 \text{ (if female)}$$

$$\times 1.159 \text{ (if black)}$$

11. Inadvertent omission of exclusion line item
12. Show a history of central nervous system conditions such as strokes, transient ischemic attacks, significant head trauma, seizures, central nervous system infections, migraine, brain surgery, or any other neurological conditions that, in the opinion of the investigator, increase the risk of participating in the study
13. Have a history or presence of neuropsychiatric disease (e.g., bipolar disorder, schizophrenia, depression) considered as clinically significant by the investigator
14. Regularly use known drugs of abuse or show positive findings on drug screening
15. Show evidence of human immunodeficiency virus infection and/or positive human immunodeficiency virus antibodies
16. Presence of hepatitis B surface antigen at screening or within 3 months prior to first dose of study intervention
17. Positive hepatitis C antibody test result at screening or within 3 months prior to first dose of study intervention.
NOTE: Participants with positive hepatitis C antibody due to prior resolved disease can be enrolled if a confirmatory negative hepatitis C RNA test is obtained
18. Positive hepatitis C RNA test result at screening or within 3 months prior to first dose of study intervention.
NOTE: Test is optional and participants with negative hepatitis C antibody test are not required to also undergo hepatitis C RNA testing
19. Have donated blood of more than 500 mL within the previous 2 months of study screening
20. Have any medical conditions, medical history, or are taking any medications which are contraindicated in the selpercatinib label

Prior/Concomitant Therapy

21. Have participated, within the last 30 days of admission, in a clinical study involving an investigational product. If the previous investigational product has a long half-life, 5 half-lives or 30 days (whichever is longer) should have passed.
22. Have previously completed or withdrawn from this study or any other study investigating selpercatinib, and have previously received the investigational product

23. Use of H₂ blockers, proton pump inhibitors, and other drugs that affect selpercatinib exposure within 7 days of screening
24. Are intending to use over-the-counter or prescription medication, including dietary supplements, within 14 days prior to dosing and until study discharge (apart from occasional acetaminophen (≤ 2 g/24 hours), hormonal contraception, or hormone replacement therapy)

Prior/Concurrent Clinical Study Experience

25. Are currently enrolled in any other clinical study involving an investigational product or any other type of medical research judged not to be scientifically or medically compatible with this study

Other Exclusions

26. Have an average weekly alcohol intake that exceeds 21 units per week (males ≤ 65 years old) and 14 units per week (females); 1 unit = 12 oz or 360 mL of beer; 5 oz or 150 mL of wine; 1.5 oz or 45 mL of distilled spirit(s)
27. Are unwilling to stop alcohol consumption 48 hours prior to each admission to the CRU, and while resident at the CRU. At all other times, participants must agree to consume no more than 2 units per day
28. Are smokers of more than 10 cigarettes or e-cigarettes, or 3 cigars or 3 pipes, per day and are unable to refrain from smoking while resident at the CRU
29. Unwilling to stop caffeine consumption 48 hours prior to admission and while resident at the CRU. Excessive amount is defined as greater than 6 servings (1 serving is approximately equivalent to 120 mg of caffeine).
30. Are unable to consume a standard meal (e.g., breakfast, lunch, dinner, and snack).
31. Currently use or show evidence of substance abuse (including alcohol abuse) or dependence within the past 6 months based on medical history at screening visit
32. Inability to comply with the dietary regimen of the CRU
33. Are Lilly employees or are an employee of any third-party involved in the study who require exclusion of their employees
34. Are investigator site personnel directly affiliated with this study and/or their immediate families. Immediate family is defined as a spouse, parent, child, or sibling, whether biological or legally adopted
35. In the opinion of the investigator or sponsor, are unsuitable for inclusion in the study

5.3. Lifestyle Considerations

Throughout the study, participants may undergo medical assessments and review of compliance with requirements before continuing in the study.

5.3.1. Meals and Dietary Restrictions

During the confinement period, participants will consume only food and beverages that are provided to them by the CRU staff. Standard meals (e.g., breakfast, lunch, dinner, and snack) will be provided to the participants while resident at the CRU.

In both Stages 1 and 2 of the study, selpercatinib will be dosed in the fasted state on Day 1 and Day 15.

On dosing occasions, the participants will be fasted overnight (at least 10 hours) prior to dosing and refrain from consuming water from 1 hour predose until 2 hours postdose, excluding the amount of water consumed during introduction of the NG tube and at dosing. Food is allowed from 4 hours postdose. At all other times during the study, participants may consume water ad libitum.

Foods and beverages containing poppy seeds, grapefruit, or Seville oranges will not be allowed from 7 days prior to check-in until discharge from the study.

5.3.2. Caffeine, Alcohol, and Tobacco

Participants will abstain from ingesting caffeine- or xanthine-containing products (e.g., coffee, tea, cola drinks, and chocolate) for 48 hours prior to Day -1 until after discharge from the study.

Participants will abstain from alcohol for 48 prior to Day -1 until after discharge from the study.

Participants who use tobacco products will be instructed that use of nicotine-containing products (including nicotine patches) will not be permitted while they are in the clinical unit.

5.3.3. Activity

Participants will abstain from strenuous exercise for 48 hours before each blood collection for clinical laboratory tests. Participants may participate in light recreational activities during the study (e.g., watching television, reading).

5.4. Screen Failures

Screen failures are defined as participants who consent to participate in the clinical study but are not subsequently assigned to study intervention.

Individuals who do not meet the criteria for participation in this study (screen failure) may not be rescreened. Repeating of laboratory tests during the screening period or repeating screening tests to comply with the protocol designated screening period does not constitute rescreening.

6. Study Intervention(s) and Concomitant Therapy

Study intervention is defined as any investigational intervention(s), marketed product(s), placebo, or medical device(s) intended to be administered to/used by a study participant according to the study protocol.

6.1. Study Intervention(s) Administered

Table JZJZ.6.1. Study Interventions Administered

Study Intervention	Selpercatinib	Selpercatinib
Dosage Formulation	Capsule	Tablet
Unit Dose Strength/Dosage Level	2 × 80-mg capsules (160 mg selpercatinib)	1 × 160-mg tablets (160 mg selpercatinib)
Route of Administration	Oral	Oral
Dosing Instructions	2 capsules taken on Day 1 or Day 15, according to the randomization schedule	1 tablet taken on Day 1 or Day 15, according to the randomization schedule

6.1.1. Administration Details

A single oral dose of selpercatinib 160-mg will be administered in the morning of Days 1 and 15 with approximately 240 mL of room temperature water while in a sitting position. Participants will not be allowed to lie supine for 2 hours after dosing, unless clinically indicated or for study procedures.

Selpercatinib capsules and tablets should be swallowed whole. Participants should not break, crush, or chew the capsules or tablets, and should not empty the contents of the capsules.

On dosing days, participants will adhere to meal restrictions as outlined in Section 5.3.1.

6.2. Preparation, Handling, Storage, and Accountability

1. The investigator or designee must confirm appropriate storage conditions have been maintained during transit for all study intervention received and any discrepancies are reported and resolved before use of the study intervention.
2. Only participants enrolled in the study may receive study intervention. Only authorized study personnel may supply, prepare, or administer study intervention. All study intervention must be stored in a secure, environmentally controlled, and monitored (manual or automated) area in accordance with the labeled storage conditions with access limited to the investigator and authorized study personnel.
3. The investigator or authorized study personnel are responsible for study intervention accountability, reconciliation, and record maintenance (i.e., receipt, reconciliation, and final disposition records).
4. Further guidance and information for the final disposition of unused study interventions are provided in the study reference manual.

Note: in some cases, sites may destroy the material if the evaluator has verified and documented that the site has appropriate facilities and written procedures to dispose of clinical materials.

Samples of the specific batches of selpercatinib used in the study will be retained; details will be provided separately.

6.3. Measures to Minimize Bias: Randomization and Blinding

This is an open-label study. There is no bias as the primary endpoint is PK and objective in measure.

In both Stages 1 and 2, participants will be assigned a unique number (randomization number) on Day 1. The randomization number encodes the participant's assignment to be dosed with either the capsule or tablet on Days 1 and 15 according to the randomization schedule generated prior to the study by the Statistics Department at Covance.

6.4. Study Intervention Compliance

Participants are dosed at the site and will receive study intervention directly from the investigator or designee, under medical supervision. The date and time of each dose administered in the clinic will be recorded in the source documents and recorded in the eCRF. The dose of study intervention and study participant identification will be confirmed at the time of dosing by a member of the study site staff other than the person administering the study intervention. Study site personnel will examine each participant's mouth to ensure that the study intervention was ingested.

6.5. Dose Modification

Dose modification will not be permitted in this study.

6.6. Continued Access to Study Intervention After the End of the Study

Selpercatinib will not be made available to participants after completion of the study.

6.7. Treatment of Overdose

For the purposes of this study, an overdose of selpercatinib is considered as any dose higher than the dose assigned. There is no specific antidote for selpercatinib.

In the event of an overdose, the investigator/treating physician should:

1. Contact the medical monitor immediately.
2. Closely monitor the participant for any AE/Serious adverse events (SAE) and laboratory abnormalities until study intervention can no longer be detected systemically (at least 5 days).
3. Document the quantity of the excess dose as well as the duration of the overdose in the eCRF.

Decisions regarding dose interruptions will be made by the investigator in consultation with the medical monitor based on the clinical evaluation of the participant.

6.8. Concomitant Therapy

Any medication or vaccine (including over-the-counter or prescription medicines, vitamins, and/or herbal supplements) that the participant is receiving at the time of enrollment or receives during the study must be recorded along with:

- a. Reason for use
- b. Dates of administration including start and end dates
- c. Dosage information including dose and frequency for concomitant therapy of special interest

The medical monitor should be contacted if there are any questions regarding concomitant or prior therapy.

Participants must abstain from taking prescription or nonprescription drugs (including vitamins and dietary or herbal supplements) within 14 days before the start of study intervention until discharge from the study.

Acetaminophen, at doses of \leq 2 grams/24 hours, is permitted for use at the discretion of the investigator for the treatment of headache, etc. Contraceptive medication is permitted as per the contraception requirements (Appendix 4 [Section 10.4]), and hormone replacement therapy is also allowed.

Other medication may be considered on a case-by-case basis by the investigator in consultation with the Lilly clinical pharmacologist (CP)/clinical research physician (CRP), or designee.

7. Discontinuation of Study Intervention and Participant Discontinuation/Withdrawal

Participants discontinuing from study intervention prematurely for any reason should complete AE and other early discontinuation procedures as per the SoA (Section 1.3).

Participants discontinuing from the study prematurely for any reason must complete AE and early discontinuation procedures as per the SoA (Section 1.3).

Discontinuation of the study as a whole is described in Appendix 1 (Section 10.1).

[figure not shown]
7.1. Discontinuation of Study Intervention

In rare instances, it may be necessary for a participant to permanently discontinue study intervention. If study intervention is permanently discontinued, the participant will remain in the study to be evaluated for safety. See the SoA for data to be collected at the time of discontinuation of study intervention and discharge from the study, and for any further evaluations that need to be completed.

7.1.1. Liver Chemistry Stopping Criteria

Study intervention will be discontinued **for a participant** if liver chemistry stopping criteria are met.

Phase 1 Liver Chemistry Stopping Algorithm

Abbreviations: ALT = alanine transaminase; INR = international normalized ratio; SAE = serious adverse event; ULN = upper limit of normal.

Liver Safety: Suggested Actions and Follow-up Assessments can be found in Appendix 6 (Section 10.6).

7.1.2. QTc Stopping Criteria

A participant who meets either bulleted criterion following single ECG assessment should have ECG repeated. If the participant still meets either bulleted criterion they will be withdrawn from the study.

- QTc, QTcB, QTcF >500 msec
- Change from baseline: QTc >60 msec

If a clinically significant finding is identified (including, but not limited to changes from baseline in QTc using Bazett's formula or QTcF) after enrollment, the investigator or qualified designee will determine if the participant can continue in the study and if any change in participant management is needed. This review of the ECG printed at the time of collection must be documented. Any new clinically relevant finding should be reported as an AE.

See the SoA for data to be collected at the time of intervention discontinuation and discharge from the study, and for any further evaluations that need to be completed.

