2.2. Background

Selpercatinib (LY3527723) is a highly potent and specific small-molecule inhibitor of the RET kinase, with minimal inhibition of other kinase and nonkinase targets.

Selpercatinib doses have been evaluated in healthy participants or patients with advanced or metastatic RET-mutant MTC, advanced or metastatic RET fusion-positive thyroid cancer, other RET fusion-positive solid tumors, and metastatic RET fusion-positive NSCLC across Phase 1, 2, and 3 clinical studies. Across these studies, single oral doses of selpercatinib were administered over a range of 20 to 720 mg. Multiple oral doses of 160 mg/day selpercatinib were administered orally twice daily for 10 days in healthy volunteers. The most frequently reported ($\geq 15\%$ of participants regardless of attribution to study drug) Adverse events (AEs) in the ongoing first-in-human dose finding study were dry mouth, diarrhea, hypertension, AST/ALT increased, fatigue, constipation, edema peripheral, nausea, headache, blood creatinine increased, abdominal pain, rash, ECG QT prolonged, cough, vomiting, and dyspnea.

The median t_{max} of selpercatinib is 2 hours and is slowly eliminated with a mean $t_{1/2}$ of approximately 32 hours in healthy volunteers. More detailed information about the PK and absorption, distribution, metabolism, and excretion properties of selpercatinib may be found in the IB.

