4.1.2. Treatment and Assessment Period

Stage 1:

Participants will be admitted to the CRU on Day -1. On the morning of Day 1, participants will be randomized to receive a single oral dose of 160-mg selpercatinib as the capsule or tablet formulation, and will be dosed according to the randomization sequence following an overnight fast of at least 10 hours. On Day 1, participants will have an NG tube placed in the stomach prior to dosing to assess gastric pH, as outlined in Section 8.5. Participants will remain resident at the CRU until discharge on Day 7.

Participants will attend outpatient visits for the collection of PK blood samples and assessment of vital signs on Days 9 and 11.

Participants will be re-admitted to the CRU on Day 14 and in the morning of Day 15 will receive their second single oral dose of 160-mg selpercatinib as the capsule or tablet formulation, according to the randomization schedule, following an overnight fast of at least 10 hours. On Day 15, participants will have an NG tube placed in the stomach prior to dosing to assess gastric pH. Participants will remain resident at the CRU until discharge on Day 21.

Participants will attend outpatient visits for the collection of blood samples and assessment of vital signs on Days 23, 25, and 28.

There will be a washout of at least 14 days between doses of selpercatinib.

Stage 2:

Participants will be admitted to the CRU on Day -1. On the morning of Day 1, participants will be randomized to receive a single oral dose of 160-mg selpercatinib as the capsule or tablet

formulation, and will be dosed according to the randomization sequence following an overnight fast of at least 10 hours. Participants will remain resident at the CRU until discharge on Day 7.

Participants will attend outpatient visits for the collection of PK blood samples and assessment of vital signs on Days 9 and 11.

Participants will be re-admitted to the CRU on Day 14 and in the morning of Day 15 will receive their second single oral dose of 160-mg selpercatinib as the capsule or tablet formulation, according to the randomization schedule, following an overnight fast of at least 10 hours. Participants will remain resident at the CRU until discharge on Day 21.

Participants will attend outpatient visits for the collection of blood samples and assessment of vital signs on Days 23, 25, and 28.

There will be a washout of at least 14 days between doses of selpercatinib.

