7.2. Participant Discontinuation/Withdrawal from the Study

A participant may withdraw from the study:

- at any time at his/her own request
- at the discretion of the investigator for safety, behavioral, compliance, or administrative reasons
- if the participant becomes pregnant during the study
- if enrollment in any other clinical study involving an investigational product or enrollment in any other type of medical research judged not to be scientifically or medically compatible with this study
- if the participant, for any reason, requires treatment with another therapeutic agent that has been demonstrated to be effective for treatment of the study indication, discontinuation from the study occurs prior to introduction of the new agent.

Discontinuation is expected to be uncommon.

At the time of discontinuing from the study, if possible, an early discontinuation visit should be conducted, as shown in the SoA. See SoA for data to be collected at the time of study discontinuation and discharge from the study, and for any further evaluations that need to be completed. The participant will be permanently discontinued from both the study intervention and the study at that time.

If the participant withdraws consent for disclosure of future information, the sponsor may retain and continue to use any data collected before such a withdrawal of consent. If a participant withdraws from the study, he/she may request destruction of any samples taken and not tested, and the investigator must document this in the site study records.

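### Section 7.1.2 withdraws a confirmed QTc case from the study, while its parent Section 7.1 keeps anyone taken off study drug in the study for safety evaluation; no exception is stated

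*Protocol*

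**What the plan says.** Section 7.1 of the protocol deals with stopping study drug. Its general rule carries no condition: "If study intervention is permanently discontinued, the participant will remain in the study to be evaluated for safety".

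Two subsections sit beneath it. Section 7.1.1 (liver chemistry) has study drug stopped when its criteria are met. Its text does not remove the participant from the study. Section 7.1.2 (QTc) has two criteria: an interval above 500 msec, or a rise of more than 60 msec from baseline. The ECG is repeated, and then: "If the participant still meets either bulleted criterion they will be withdrawn from the study".

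Section 7.2 says what leaving the study means: "The participant will be permanently discontinued from both the study intervention and the study at that time". It asks for one early discontinuation visit, if possible. The opening of Section 7 applies similar procedures to those who only stop the drug: "Participants discontinuing from study intervention prematurely for any reason should complete AE and other early discontinuation procedures as per the SoA".

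Section 8.2.4 refers back to Section 7 and calls the QTc rules withdrawal criteria.

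**The concern.** A rule placed under the heading for stopping study drug would be expected to follow that heading's general statement or to say that it departs from it. The QTc rule does neither. A site with a confirmed QTc finding after the Day 1 dose therefore has one instruction to keep the participant under safety evaluation and another to end participation.

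The point at stake is participant safety. QT prolongation is listed in Sections 2.2 and 2.3 among the frequent adverse events in the first-in-human study and the common toxicities in patients. The ECG at 2 h falls at the median tmax that Section 2.2 gives, and the drug is "slowly eliminated with a mean $t_{1/2}$ of approximately 32 hours in healthy volunteers". Ending participation then stops planned safety checks and routine recording of new adverse events early in the exposure.

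**Working it through.** There is no planned figure to reproduce. The check compares the rules, with one short calculation on timing.

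1. **Does the QTc rule trigger the general rule?** Section 6.1.1 fixes the dosing days: "A single oral dose of selpercatinib 160-mg will be administered in the morning of Days 1 and 15". By Section 7.2, withdrawal from the study also ends study drug. A participant withdrawn after the Day 1 dose and before the Day 15 dose therefore loses a planned dose for good. That is the situation Section 7.1 describes.

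2. **Can both be followed in that window?**

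| Rule | Further dose? | Still in the study? |
|---|---|---|
| 7.1, general | No | Yes, for safety evaluation |
| 7.1.1, liver | No | Nothing in its text departs from 7.1 |
| 7.1.2, confirmed QTc | No (through 7.2) | No |

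   The rules agree that dosing stops and disagree on whether the participant stays.

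3. **Is an exception stated anywhere?** The opening of Section 7, then 7.1, 7.1.1, 7.1.2, 7.2, 8.2.4 and the Schedule of Activities were compared. None says that QTc cases fall outside 7.1. The closing sentence of 7.1.2 points to the Schedule both for stopping the drug and for discharge, so it fits either reading.

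4. **Which scheduled ECGs fall in the window?** As far as the Schedule can be read, they are Day 1 at 2 h, Day 2, and Day 15 predose. Unscheduled ECGs may add to these.

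5. **How far has elimination gone at each?** Half-lives elapsed = hours since dose / 32.
   - Day 1, 2 h: 2/32 = 0.06.
   - Day 2, assuming about 24 h after dosing (the Schedule gives no hour): 24/32 = 0.75. This is less than one half-life, so under log-linear decline more than half remains.
   - Day 15 predose: 14 × 24 = 336 h, and 336/32 = 10.5. The conflict between the rules stands, but the point about drug still to be eliminated does not apply.

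6. **What does following 7.1.2 end?** On the planned schedule, "Participants will remain resident at the CRU until discharge on Day 7", with outpatient vital signs on Days 9 and 11 (Section 4.1.2) and further safety laboratory tests. Under Section 8.3.1, routine adverse event collection stops when participation ends.

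7. **What continues anyway?** There is an early discontinuation visit where possible, and the Schedule's early discontinuation column includes an ECG. Section 8.2.4 allows extra ECGs. Section 8.3 keeps the investigator responsible for events that led to discontinuation, and Section 10.3.4 requires medically indicated evaluations. Follow-up of the QTc event itself is therefore covered. The planned safety checks and routine recording of new adverse events are not.

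**The case against.** The strongest reply is that the intent is readable. A specific, mandatory rule normally governs a general one, Section 8.2.4 also speaks of withdrawal, and Section 7.2 allows withdrawal for safety. On this view only a cross-reference is missing. Withdrawal may also look like the cautious choice for healthy volunteers with no expected benefit.

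Part of this stands: withdrawal may well be what was meant. But Section 7.1 has no carve-out, so the texts still conflict. The caution lies in giving no further dose, and that does not require ending observation.

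The reply is stronger on size. Section 7.1 promises safety evaluation, not a fixed set of visits, and the Schedule has no separate track for someone off drug but still enrolled. Few scheduled ECGs remain after the 2 h reading: one on Day 2, then none until the next dosing day, as far as the table can be read. These points stand and limit the claim.

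A reader might also cite the next paragraph of 7.1.2, where "the investigator or qualified designee will determine if the participant can continue in the study", as a second contradiction. It covers clinically significant ECG findings in general. Discretion over that wider group does not clearly displace a mandatory rule for confirmed threshold cases, so nothing here rests on it.

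**Conclusion.** The conflict is real but narrow. It concerns confirmed QTc events after the Day 1 dose and before the Day 15 dose. In that window 7.1 and 7.1.2 cannot both be followed. For events at the 2 h or Day 2 ECG, 7.1.2 ends scheduled safety assessments and routine collection of new adverse events while most of the drug is still to be eliminated. This rests on the stated half-life and, for Day 2, on an ECG at about 24 h.

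No number of cases can be given. The documents give no QTc event rate in healthy participants, and Section 7.2 expects discontinuation to be uncommon.

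Four stronger readings are tempting, and the documents do not support them:

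- **That every remaining visit and blood sample in the period is lost against what 7.1 promises.** Section 7.1 sets no visit schedule and says nothing about pharmacokinetic sampling.
- **That the same conflict exists after the Day 15 dose.** No dose is then left to stop, so 7.1 is arguably not triggered. Whether to withdraw at that point is a design preference.
- **That the QTc finding itself would go unfollowed.** Sections 8.2.4, 8.3 and 10.3.4 already provide for it.
- **That the bioequivalence conclusion is affected.** No such effect is claimed.

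**What to change.** Make two edits in a protocol amendment:

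1. In 7.1.2, replace the withdrawal clause so that participants who still meet a criterion on repeat *will be permanently discontinued from study intervention (no further dose) and will remain in the study for safety evaluation per Section 7.1, with ECGs repeated as clinically indicated until the finding resolves or stabilises*.
2. In 8.2.4, change *QTc withdrawal criteria* to *QTc stopping criteria*.

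This keeps the protection against a further dose and brings the QTc rule into line with the liver rule. The early discontinuation procedures can stay where Section 7 places them, and no pharmacokinetic sampling needs to be added.

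If withdrawal is intended, the minimum is to add an exception for Section 7.1.2 to the sentence in 7.1. That removes the conflict but not the loss of observation.

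The cost is the wording and a few extra safety visits in rare cases. Sample size, alpha and the SAP do not change.
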